#### **6.1.10. Data Adjustments/Handling/Conventions**

All collected data will be presented in listings. Data not subject to analysis according to this plan will not appear in any tables or graphs but will be included in the data listings.

All p-values will be displayed in four decimals and rounded using standard scientific notation (e.g., 0.XXXX). A p-value less than 0.0001 will be shown in tables as <0.0001.

#### 6.1.10.1. **Missing or Partial Dates/Times for Adverse Events (AE) and Prior/Concomitant Medications (CM), AE Intensity, and AE Relationship**

The following list describes how partially missing date information will be handled as it relates to partial or missing AE start dates. Partial AE start dates will be imputed as the following:

1. If year is not missing and is after the year of first dose:
  - a. If month is missing, then month will be imputed as January.
  - b. If day is missing, then day will be imputed as the first of the month.
2. If year is not missing and is the same as the year of the first dose:
  - a. If month is missing, then impute the month as the month of the first dose date.
  - b. If day is missing, and the month is the same as the month of the first dose date, then impute day as the day of the first dose date.
  - c. If day is missing but month is after the month of first dose date, then impute day as the first day of the month.
3. If year is missing then impute the year as the year of the first dose date:
  - a. If month is missing, then impute the month as the month of the first dose date.
  - b. If day is missing, then impute the day as the day of the first dose date.
4. If the start date is completely missing, but the AE is either ongoing or the stop date is after the first dose date then impute the start date as the first dose date.
5. For any cases involving the rules above, if the AE end date is before the AE start date, then leave the AE start date missing and assume that AE is treatment emergent for the purpose of the analysis. Further, if the AE stop date is complete and occurs prior to first dose date, leave the AE start date missing and assume that AE is not treatment emergent.

Dates will not be imputed if not considered potentially treatment-emergent. For example, if the AE year matches that of the first dose date but the AE month is prior to that of the first dose date the event is not considered potentially treatment-emergent and no imputed date will be assigned. No imputations will be applied to AE stop dates. No imputations will be applied to AE start or stop times.

Imputation for medication start dates will be handled similarly.

Relationship of the AE to study intervention and intensity will not be imputed for analyses.

#### 6.1.10.2. **Missing/Partial Dates for PH Diagnosis**

PH diagnosis dates with partial dates will be imputed as follows: missing day values will be imputed as 15, and missing month values will be imputed as June in order to calculate the time since PH diagnosis or other related variables.

### 6.1.10.3. Missing Height/Weight Measurements to be Used for BSA Adjusted Uox Calculations

If the height and weight are not available from the same visit as the 24-hour Uox value, then the following imputation rules will be used to impute the height and weight in order to calculate the BSA Adjusted Uox values. Please note that the imputed height and weight values will not be summarized in any tables or provided in any listings. These imputed values will be used for the BSA Adjusted Uox calculations only.

#### Weight Imputations Rules for BSA Adjusted Uox Calculation

For all participants, regardless of age, missing weight values will be imputed by fitting a mixed model with weight at the dependent variable and study month as the main effect. Random coefficients will be used for the intercept and study month. In this way, the coefficients will vary by subject. The fitted line will be used to impute the missing weight value for a given value of study month. Example SAS pseudo code is shown below:

```
ODS OUTPUT SolutionF = fixed SolutionR = random
PROC MIXED DATA=weightdata;
CLASS <subject>;
MODEL <weight> = <study month> / SOLUTION;
RANDOM INTERCEPT <study month> / SUBJECT = <subject> SOLUTION;
RUN;

PROC TRANSPOSE DATA = fixed (KEEP = estimate effect) OUT = fixed1 (DROP = _name_
RENAME = (<study month> = fmonth <intercept> = fintercept));
ID effect;
RUN;

PROC TRANSPOSE DATA = random (KEEP = <subject> estimate effect) OUT = random1
(DROP = _name_);
BY <subject>;
ID effect;
RUN;

DATA coefficients;
IF _n_ = 1 THEN SET fixed1;
SET random1;
<intercept> = fintercept + intercept;
<month slope> = fmonth + <study month>;
RUN;
```

To calculate a missing weight value from a known study month, take the corresponding subject specific coefficients from the dataset above and plug them into the formula  $\langle \text{weight} \rangle = \langle \text{intercept} \rangle + \langle \text{month slope} \rangle * \langle \text{study month} \rangle$ .

### Height Imputation Rules for BSA Adjusted Uox Calculation:

- For participants <18 years, missing height values will be imputed in the same way as described above for weight except that height will be the dependent variable for the model.
- For adults ( $\geq 18$  years), height at screening will be used for BSA adjusted Uox calculation. Height will not be imputed for post-screening visits.

### 6.1.11. Subgroups

The same analysis for the primary endpoint (i.e.  $AUC_{24\text{-hour } U_{ox}}$  from Day 90 to Day 180, based on percent change from baseline) will be performed on the subgroup of participants with at least one baseline 24-hour  $U_{ox} \geq 1.6$  mmol (adjusted per  $1.73 \text{ m}^2$  BSA in participants aged <18 years).

Subgroup analysis of the primary endpoint may be performed on the list of subgroups provided in Table 2, if data permitting.

**Table 2: List of Subgroups**

|   |
|---|
| 1. Age (6 to 11 years if available, 12 to 17 years, or $\geq 18$ years)     |
| 2. Baseline eGFR (<45 mL/min/surface area or $\geq 45$ mL/min/surface area) |
| 3. PH Type (PH1 or PH2)   |
| 4. Gender (male or female)  |

## 7. Study Participants and Demographics

### 7.1. Disposition of Participants and Withdrawals

Disposition will include tabulations by treatment group and over-all for the number of participants enrolled, and either screen failed or randomized into each treatment group. The number and percentage of participants who: received treatment, completed treatment, completed study, reasons for treatment discontinuation/study withdrawal (overall and by reason for discontinuation/study withdrawal), and continue on to protocol DCR-PHXC-301 will be reported by treatment group and overall. The number and percentage of participants in each analysis population will also be displayed by treatment group and overall.

### 7.2. Protocol Violations and Deviations

Prior to database lock and unblinding, all protocol deviations will be reviewed and categorized as either 'Important' or 'Non-important':

- Important PDs are a subset of protocol deviations that may significantly impact the completeness, accuracy, and/or reliability of key study data or that may significantly affect a subject's rights, safety, or well-being.
- Non-important PDs will be identified as any protocol deviation that does not meet the criteria for Important PD.

Subjects with at least 1 deviation classified in the major protocol deviation list included in the appendix to this SAP will be excluded from the PP analysis population.

### 7.3. Demographics and Other Baseline Characteristics

Summary statistics for age, age category, gender, race, ethnicity (where available, as ethnicity may not be collected at all sites), height, weight, and BSA will be presented by treatment group and overall. Body mass index will be calculated at the site and recorded in the eCRF. Body surface area will be computed as described in Section 6.1.10.

Summary statistics will be presented by treatment group and overall for baseline eGFR category, baseline 24-hour Uox results, PH type, time since PH diagnosis, number of kidney stone events in the last 12 months, and the number and surface area of kidney stones at baseline.

These summaries will be conducted for the MITT and SAF populations.

The number and percentage of participants reporting various medical histories, grouped by medical dictionary for regulatory activities (MedDRA) system organ class (SOC) and preferred term (PT) (MedDRA; Version 23.0 or higher), will be tabulated by treatment group and overall. This analysis will be conducted for the SAF population.

Prior medications will be presented separately from concomitant medications. Medications that started prior to dosing on Day 1 will be considered prior medications whether or not they were stopped prior to Day 1 dosing. Missing dates will be handled using the methodology described in Section 6.1.11.1. Medications will be coded using world health organization drug dictionary (WHO-DD) version B3 September, 2019 or higher. The number and percentage of participants reporting prior medication use, grouped by ATC Level 2 and ATC Level 4, will be tabulated by treatment group and overall. This analysis will be conducted for the SAF population. A listing of prior medications will be provided; the analysis on concomitant medications is described in Section 9.7.

All collected demographics and other baseline characteristics will be listed by participant.

### 7.4. Exposure and Compliance

Study intervention will be administered in clinic once monthly as described in Section 3.4. Any deviations from the planned dose will be reported.

Summary statistics of the number of doses received, the number of participants who received study drug for each dosing visit, and the percent of scheduled doses received will be presented by treatment group.

These summaries will be conducted for the SAF population. All study drug administration information will be presented in participant data listings.

## 8. Efficacy Analysis

All AUC parameters referenced in the efficacy analysis refer to the standardized AUCs defined in section 6.1.9.

### 8.1. Primary Efficacy Analysis

The primary efficacy endpoint of this study is the  $AUC_{24\text{-hour } U_{ox}}$  from Day 90 to Day 180, based on percent change from baseline. The primary endpoint will be compared between the active treatment group and the placebo group.

This is a superiority study. For the primary endpoint, the null hypothesis to be tested is:

- $H_0: AUC_{24\text{-hour } U_{ox, a}} = AUC_{24\text{-hour } U_{ox, p}}$  against one-sided alternative hypothesis
- $H_A: AUC_{24\text{-hour } U_{ox, a}} > AUC_{24\text{-hour } U_{ox, p}}$ .

where

- $AUC_{24\text{-hour } U_{ox, a}}$  is the  $AUC_{24\text{-hour } U_{ox}}$  for the active treatment arm (DCR-PHXC),
- $AUC_{24\text{-hour } U_{ox, p}}$  is the  $AUC_{24\text{-hour } U_{ox}}$  for the placebo arm

All hypotheses will be tested at the one-sided significance level alpha of 2.5%.

Mean  $AUC_{24\text{-hour } U_{ox}}$  from Day 90 to Day 180 will be compared between treatment groups using an ANCOVA model with treatment group as a main effect in the model; and age category [6 to 11, 12 to 17, or  $\geq 18$  years], eGFR category [ $< 45$  mL/min or  $\geq 45$  mL/min], and baseline  $U_{ox}$  as covariates, where the BSA adjustment is applied to the 24 hour urinary oxalate values for all pediatric subjects. The adjusted means for each treatment will be presented together with their 95% confidence intervals. The adjusted mean difference will be presented along with its 95% confidence interval and p-value.

The primary efficacy analysis will be based on the MITT dataset. This analysis will be repeated for the PP population and in addition as sensitivity analyses in ITT and EVAL population (see section 8.5).

$U_{ox}$  concentrations which do not meet completeness criteria (see section 6.1.5.2) will be excluded from the primary efficacy analysis. Multiple imputation will be used for those excluded values as well as for all other missing values.

Descriptive statistics for actual  $U_{ox}$  concentrations and for percent change from baseline will be presented by visit.

### 8.2. Key Secondary Efficacy Analysis

The key secondary endpoint of the proportion of participants whose  $U_{ox}$  values normalized or near-normalized on at least 2 consecutive visits starting at Day 90 will be summarized by

treatment group. A one-sided Fisher's exact test at significance level alpha of 2.5% will be used for comparison between treatment groups within the hierarchical testing framework described in section 6.1.4 Multiple Comparisons.

Two separate analyses of the key secondary efficacy endpoint will be presented:

1. Primary analysis: applying the BSA Uox adjustment only to subjects < 18 years old
2. Secondary (sensitivity) analysis: applying the BSA Uox adjustment to all subjects (pediatrics and adults)

The analyses will be performed based on MITT population.

### 8.3. Secondary Efficacy Analysis

[figure not shown]
The secondary efficacy endpoints listed below will be summarized by treatment group. A one-sided Wilcoxon Rank Sum test will be used for the comparison between treatment groups for both change and percentage change from baseline for the following outcome variables.

- Change/Percentage change from baseline to Day 180 in the summed surface area of kidney stones
- Change/Percentage change from baseline to Day 180 in the number of kidney stones
- Change/Percentage change from baseline to Day 180 in plasma oxalate (for adults only)

The stone surface area and stone count are defined as follows:

- Stone Surface Area: sum of the measured and calculated surfaces of the stone larger than 5 mm (the longest diameter)
- Stone Count: Stones will be categorized measurable or non-measurable as follows, only measurable stones will be used in the analyses:
  - Measurable : with a minimum size of 5 mm in the longest diameter the surface area of the stones
  - Non Measurable: all other stones, including small stones (longest diameter < 5 mm); if the number is too high, they may just say "too many to count", and / or provide an approximate number

Percentage change will also be calculated for the summed surface area of kidney stones and number of kidney stones using the CT results. These will be listed for each subject for the subgroup of participants from CT sub-study as described in the Protocol Appendix B.

A linear mixed model with observed eGFR as the dependent variable and treatment, study month and the interaction between treatment and month as independent variable, will be used to estimate rate of decline in eGFR response between DCR-PHXC and placebo treatments. A random intercept and slope will be included in the mixed model to fit a different intercept and slope for each subject. In this analysis nominal month will be modeled as a continuous independent factor.

The Least Squares adjusted means will be reported for each treatment group as well as the standard errors and 95% confidence intervals for the LS means. The estimate of treatment effect will be reported as the difference in treatment means, 95% confidence interval for the difference in means, the standard error for the mean difference, and the p-value for the treatment difference.

Example SAS code is provided below for reference:

```
PROC MIXED DATA= METHOD=REML;  
  CLASS <treatment> <participant ID>;  
  MODEL <observed eGFR value> = <treatment> <Month> <treatment*Month> / SOLUTION  
  DDFM=KWR;  
  RANDOM int <Month> / SUB= <participant ID> TYPE=<covariance structure>;  
  ESTIMATE "Slope for Treatment='DCR-PHXC' " Month 1 <treatment*Month> 1 0 ;  
  ESTIMATE "Slope for Treatment='Placebo' " Month 1 <treatment*Month> 0 1 ;  
  ESTIMATE "DCR-PHXC versus Placebo" <treatment*Month> 1 -1 / alpha=0.05 CL;  
  RUN;
```

To handle the repeated measures data an unstructured variance-covariance matrix will be considered. In the event of convergence issues, a compound symmetric variance-covariance matrix will be used.

Separate ANOVA models will be considered for the following two eGFR parameters:

- Parameter 1: including all subjects using eGFR CKD-EPI equation and Schwartz et al. 2009 creatinine-based equation.
- Parameter 2: including all subjects using eGFR CKD-EPI equation and Schwarz 2012 Cystatin C-based equation

These analyses will be performed based on the ITT population. All hypotheses will be tested at the one-sided significance level alpha of 2.5% within the hierarchical testing framework described in section 6.1.4 Multiple Comparisons.

Descriptive statistics for the summed surface area of kidney stones, number of kidney stone, plasma oxalate, eGFR, and for the percent change from baseline will be presented by visit.

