8.1.6.1. Kidney Stone Events and Stone Burden

Participants will provide a 12-month history of stone events at Screening and will report any stone events during the study.

For the purpose of this study, “stone events” are all events that meet one or more of the following criteria:

- **renal stone requiring medical intervention** (e.g., outpatient procedures such as lithotripsy, or hospitalization and/or inpatient surgical intervention for confirmed stone-related pain and/or complications);
- **stone passage with or without hematuria;**
- **renal colic requiring medication.**

Concurrent events will be defined as events occurring within the same 4-week (28-day) window.

Note: Although the number of stone events is an efficacy endpoint, stone events will be considered AEs of special interest (Section 10.3.3), as participants may enter the study with pre-existing stones.

For the purpose of the study, “stone burden” is a term used primarily as a metric for quantifying and qualifying changes from baseline in the overall number and 2-dimensional surface area of renal stones, as observed via kidney ultrasound over the course of the study.

Taken together, the terms stone event and stone burden will be used to derive meaningful quantification and qualification of overall impact of clinical sequelae of renal stones during the course of the trial.

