8.1.6.2. Kidney Ultrasound

Kidney ultrasound will be performed at time points specified in the SoA. The kidneys should be examined in the longitudinal (sagittal) and transverse scan planes, ideally with images acquired in both the supine and prone positions. In adult participants, a curved array transducer with center frequencies of 3 to 6 MHz should be used. A linear array transducer with higher center frequencies should be used in participants younger than 18 years of age. Participants should have a full bladder during image acquisition.

[figure not shown]
All kidney ultrasound data will be transmitted to a standalone imaging vendor, where qualified personnel will perform central overread of all images. The number and size of stones will be determined by the central readers. The details of any findings should be placed in the participant’s source record and recorded in the electronic case report form (eCRF). Site personnel will be trained in the processes relating to ultrasound performance and data transmission.

The end-to-end process of centralized kidney ultrasound overread is detailed in a separate DCR-PHXC-201 Centralized Imaging Overread plan.

Centralized overread will include standardized nephrocalcinosis grading in accordance with the staging criteria outlined in **Figure 2**.

Figure 2: Standardized Nephrocalcinosis Grading

- Grade 0: No echogenicity
- Grade 1: Mild echogenicity around medullary pyramid borders
- Grade 2: Moderate echogenicity around and inside pyramids
- Grade 3: Severe echogenicity of entire pyramids

From [Boyce et al., 2013](#)

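### SAP 8.3 sums stone area over stones above 5 mm but counts stones of 5 mm or more, so a stone recorded at exactly 5 mm is counted with zero area

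*SAP*

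**What the plan says.** SAP Section 8.3 names two stone-burden outcomes: "Change/Percentage change from baseline to Day 180 in the summed surface area of kidney stones" and "Change/Percentage change from baseline to Day 180 in the number of kidney stones". It then defines each one.

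- **Area:** the "sum of the measured and calculated surfaces of the stone larger than 5 mm (the longest diameter").
- **Count:** stones are split into measurable and non-measurable, and "only measurable stones will be used in the analyses". Measurable stones are those "with a minimum size of 5 mm in the longest diameter the surface area of the stones". Non-measurable stones are "all other stones, including small stones (longest diameter < 5 mm").

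Both outcomes are compared by a one-sided Wilcoxon rank sum test. In SAP Section 6.1.4, percent change in number is fourth and percent change in area fifth in the hierarchical sequence, each at one-sided 0.025.

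Protocol Section 8.1.6.1 describes stone burden through "changes from baseline in the overall number and 2-dimensional surface area of renal stones" on ultrasound and sets no size limit. Protocol Section 8.1.6.2 says that "The number and size of stones will be determined by the central readers" and gives no measurement precision. SAP Section 10 declares no changes from the planned analysis.

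**The concern.** The two outcomes are meant to describe the same stones on the same scan, yet the area rule is strict (above 5 mm) and the count rule is inclusive (5 mm or more). The non-measurable class, which names stones below 5 mm, confirms that a 5 mm stone belongs to the count. Such a stone therefore enters one endpoint and is dropped from the other.

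Two consequences follow. First, a small movement onto 5 mm can be recorded as complete loss of area. A value of -100% is the lowest that percent change can take, so in a rank test it ties with true clearance of all stones. Second, a participant whose only measurable stone is 5 mm at baseline has zero baseline area, so percent change in area cannot be computed although percent change in count can. The two tests could then rest on different participants.

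Both outcomes are in the alpha-controlled sequence of a trial planned at 24 against 12 participants. Each should have one definition that two programmers would code identically.

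**Working it through.** The plan states no expected value, power or sample size for the stone outcomes, so there is no figure to reproduce. The check applies the two SAP rules to simple cases.

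**Inputs.** Area threshold: above 5 mm (SAP 8.3). Count threshold: 5 mm or more (SAP 8.3). Percent change: 100 × (value − baseline) / baseline (SAP 6.1.9). Assumption: a circular stone with area πd²/4, because the SAP gives no area formula. The -100% for area and 0% for count in the first case do not depend on this.

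**Areas.** 5 mm: 19.6 mm². 6 mm: 28.3 mm². 8 mm: 50.3 mm². 10 mm: 78.5 mm².

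| Stones, baseline to Day 180 | Area as written (above 5 mm) | Area if 5 mm or more | Count (5 mm or more) |
|---|---|---|---|
| 6 to 5 mm, sole stone | 28.3 to 0: -100% | 28.3 to 19.6: -30.6% | 1 to 1: 0% |
| 6 to 5 mm, plus unchanged 8 mm | 78.5 to 50.3: -36.0% | 78.5 to 69.9: -11.0% | 2 to 2: 0% |
| 6 to 5 mm, plus unchanged 10 mm | 106.8 to 78.5: -26.5% | 106.8 to 98.2: -8.1% | 2 to 2: 0% |
| 5 to 6 mm, sole stone | 0 to 28.3: undefined | 19.6 to 28.3: +44.0% | 1 to 1: 0% |
| 5 to 5 mm, sole stone | 0 to 0: undefined | 19.6 to 19.6: 0% | 1 to 1: 0% |

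**Absolute change.** SAP 8.3 also tests this, and it is defined from a zero baseline, but it is distorted too. For 6 to 5 mm the rule gives -28.3 mm² where the aligned rule gives 19.6 − 28.3 ≈ -8.6 mm² (from unrounded areas). The gap is the 19.6 mm² of the dropped 5 mm stone.

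**Away from exactly 5 mm the rules agree.** A sole stone going from 6 to 5.1 mm gives -27.8% under both area rules with the count unchanged. Going from 6 to 4.9 mm gives -100% for area under both rules and -100% for count.

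**Which alignment removes the conflict.** With 5 mm or more for both, the first case gives -30.6% for area and 0% for count. With above 5 mm for both, area and count are each -100%. Either is consistent; the first matches the SAP's own measurable class.

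**The case against.** The strongest reply is that this is a wording slip. The Measurable line is visibly garbled: words about surface area run on from the size limit, as though the inclusive limit was meant to govern area as well. The lead-in about using only measurable stones refers to analyses in the plural. This may well be what was intended. But the only clear sentence about area still says larger than 5 mm, and that is what a programmer would code. A probable slip is a reason to correct the text.

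A second reply is that the rule applies equally to both arms of a blinded, centrally read outcome, so no bias is shown. That stands. No effect on type I error or power has been computed either. The area test is also confirmatory only after earlier steps in the sequence succeed.

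A reader might draw three stronger conclusions that the documents do not support.

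- **That any shift from 6 to 5 mm scores as total loss of area.** It does so only if no stone above 5 mm remains at Day 180. Protocol Section 8.1.6 describes these patients as prone to multiple stones, so the diluted cases in the table are realistic.
- **That a substantial share of stones is affected.** This depends on whether readers record whole millimetres or finer, and on the distribution of stone sizes. The documents give neither.
- **That the 5 mm limit is itself the error.** Abrupt changes when a stone crosses the limit, and undefined percent change for a participant with no measurable stone at baseline, follow from having any size limit and would survive the fix. SAP 8.3 also shows why a limit is useful: small stones may be too numerous to count.

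**Conclusion.** The inconsistency is real on the text but narrow. A stone recorded at exactly 5 mm is counted and contributes no area. In the extreme case, where no stone above 5 mm remains, a change from 6 to 5 mm is scored as -100% for area, against about -31% for a circular stone under a common limit, with no change in count. With another stone above 5 mm present the error is smaller: -36.0% against -11.0% with an 8 mm stone, and -26.5% against -8.1% with a 10 mm stone. A sole 5 mm stone at baseline makes percent change in area undefined.

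The intermediate figures rest on the circular-area assumption. The frequency of the problem is unknown because reading precision is not stated. It is confined to the two stone-burden outcomes. The primary and key secondary endpoints and the sample size are not affected.

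Separately, the 5 mm restriction narrows the protocol's description of stone burden, and SAP Section 10 does not declare it. Protocol Section 9.5 leaves analysis detail to the SAP, so this is a matter of declaring the change and does not show the restriction to be wrong.

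**What to change.** Before unblinding:

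1. In SAP Section 8.3, define stone surface area as the sum of the surface areas of all measurable stones (longest diameter ≥ 5 mm), the same set used for the count.
2. Rewrite the Measurable line so that it states the size limit alone, without the stray words about surface area.
3. In SAP Section 10, record that both outcomes are restricted to stones of at least 5 mm and that the protocol's definition of stone burden has no such limit.

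The cost is a few lines of SAP text and one inequality in the program. Central readers already determine stone size, so aligning the limits should need no new reads.
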